4.8. Study Size

Initially a sample size of 600 enrolled participants was planned for the prospective DAA-PASS cohort to capture an expected 122 HCC recurrence events through the 24 months of follow-up based on a 15% annual recurrence rate or 195 expected HCC recurrence events based on a 25% annual recurrence rate. Due to enrollment challenges, convenience sample sizes between 40 and 70 participants are expected. Based on a meta-analysis from 3 US and European sites^{8,1}, the 1-year HCC recurrence rate is estimated as 35%. Thus, example confidence bounds using the 35% 1-year HCC recurrence rate follow. Assuming the DAA HR is equal to 1.0, a sample size of 70 participants with an HCC recurrence rate of 35% per 12 months will provide two-sided 95% confidence bounds of 0.46 to 2.82. Hence, the convenience sample size of 70 will distinguish from a HR of 3.0 if there is no additional HCC recurrence risk related to DAA exposure. A

sample size of 60 participants with an HCC recurrence rate of 35% per 12 months will provide two-sided 95% confidence bounds of 0.43 to 3.10, and no upper confidence bound is calculable with sample size less than or equal to 50 participants.

The historical cohort will include approximately 400 patients from the ITA.LI.CA database who have HCV and were diagnosed with HCC after 2007 (when the database began to capture follow-up clinical and imaging data), successfully treated for BCLC Stage A HCC with curative therapy, and not treated with DAAs for their HCV infection after HCC diagnosis.

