9.7.1. General Conventions

Descriptive statistical methods for interval-scale measures will include tabulation of count, mean, standard deviation, median, and range. For categorical measures with fixed levels the number of participants will be displayed along with percentages based on participants with available results.

Time to HCC recurrence will be summarized with a life table displaying the numbers of participants at risk entering the time interval, cumulative censored participants, and cumulative proportion with events at the end of the interval. HCC recurrence status will only be evaluated when imaging for HCC is completed. Methods designed to handle interval censoring will be utilized. In addition, if applicable, the cumulative number of participants ongoing or censored by time will be provided.

Descriptive summaries of baseline information, such as demographics, disease characteristics and HCC treatment interventions, will be tabulated. Populations of interest to be displayed in the descriptive summaries are outlined in Section 9.7.2.

All statistical estimates will be reported along with corresponding 95% two-sided CIs. P-values for model parameters will be provided based on Wald statistics.

Unless otherwise specified, all statistical computations will be performed using R software or SAS software (Version 9.4. Copyright © 2012, SAS Institute Inc., Cary, NC).

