9.7.6.2. Model Parameters

To address the potential for bias in the estimation of the HR of DAA therapy associated with HCC recurrence, baseline factors are included in the risk model based on possible associations of each covariate with time-to-HCC recurrence or possible associations with time-to-DAA therapy. In addition to the time-varying DAA exposure, the model will include the following baseline covariates as available: alpha-fetoprotein (AFP) level, albumin level, platelet count, MELD score, age in years, gender, diabetes status, alcohol use/AUDIT score ≥ 7 , HCC treatment modality, and study centre. In the model, AFP level, albumin level, platelet count, MELD score, and age are interval-scale variables, whereas gender, diabetes status, alcohol use/AUDIT score ≥ 7 , HCC treatment modality, and study centre are categorical variables. Study centre will be included in the model as a random effect.

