The ITA.LI.CA database will be used to assemble data for a historical cohort of HCV-infected patients who were successfully treated for BCLC Stage A HCC with curative therapy, and not treated with DAAs for their HCV infection after HCC diagnosis. Per the ITA.LI.CA investigators, practice among the ITA.LI.CA participating hospitals was such that patients who had HCV (either treatment-naïve or previously treated with IFN-based therapy) were not treated with IFN after successful HCC treatment. A small number of recently-enrolled patients were treated with DAAs; these patients will be excluded from the historical cohort. Therefore, the patients for the historical cohort will include patients who have active HCV infection who were not treated for HCV (IFN-based or DAA-based regimens) during the follow-up period. Prior HCV treatment with IFN-based non-DAA regimens prior to HCC will be allowed. After considering the aforementioned inclusion/exclusion criteria for the prospective DAA-PASS, an initial examination of the ITA.LI.CA database indicates that there will be approximately 400 eligible patients for inclusion in the historical cohort.

The historical cohort will include similar data extracted from the ITA.LI.CA database (where available) as that collected in the prospective DAA-PASS cohort (see Section 9.3). The ITA.LI.CA database includes patient-level data on demographics (sex, age, birth province),

laboratory values, comorbid liver conditions (including but not limited to HCV status), medical history events, concomitant medication use (including hepatotoxic medications), alcohol use, staging of liver disease, HCC diagnosis and tumor characteristics, HCC treatment intervention(s), and prior interferon-based HCV treatment.

Based on a convenience sample size of 50 participants in the prospective cohort and the inclusion of approximately 400 historical cohort participants the expected 95% CI of the HR (assumed to be equal to 1.0) based on a 15% annual recurrence rate is 0.51 to 2.13, and based on a 25% annual recurrence rate is 0.57 to 1.82, and based on a 35% annual recurrence rate is 0.62 to 1.69.

Descriptive summaries for the historical cohort will be provided in similar formats provided for the prospective cohort. Statistical tests will be used to test the null hypothesis that the historical and prospective cohorts are homogeneous with respect to available demographics and baseline disease characteristics.

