9.9.2. Limitations of the Historical Cohort Comparison

The historical cohort comparison provides additional non-DAA follow-up time (particularly 12-24 months post HCC treatment), and addresses the potential for unmeasured confounders relating to timing of DAA treatment. The inclusion of the historical cohort data may be difficult to interpret if the treatment of HCC has changed from the pre-DAA to post-DAA era. While the historical comparators provide additional information on the recurrence of HCC among HCV patients, systematic differences in the characteristics of these patients from patients in the DAA-exposure cohort may exist; therefore, the addition of the historical cohort to the analysis may not address possible confounding factors related to the decision to initiate DAA therapy. Statistical adjustment for observed patient characteristics will be carried out but residual confounding may exist.

Analyses involving the historical cohort data may be further complicated by attempting to obtain complete information from older participant records, changes in imaging technology affecting the ability to assess disease progression in a similar fashion, and differences in the timing of assessments. The use of external cohort data decreases the comparability of treated and untreated patients, especially with factors the various identified and potentially unmeasurable predictors of recurrence risk. As mentioned above, bias may exist whether an internal or external comparator is used.

Homogeneity tests are proposed in order to assess the overall homogeneity of the prospective and historical cohorts. Results of these investigations can be used to assist in properly weighting the results of the secondary analyses involving data from the historical cohort against those of the primary analysis based only on the prospective DAA-PASS cohort.

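### Significance tests of homogeneity with 40 to 70 prospective patients are a poor guide to whether the historical and prospective cohorts are comparable; judge the size of each imbalance instead

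*Protocol*

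**What the plan says.** Secondary Objectives B and C pool the prospective cohort with untreated patients from the Italian historical database. To assess whether the two cohorts can be compared, protocol section 9.7.9 states: "Statistical tests will be used to test the null hypothesis that the historical and prospective cohorts are homogeneous". The list of characteristics to be tested is left open, the comparison being made "with respect to available demographics and baseline disease characteristics". Section 9.9.2 repeats the plan ("Homogeneity tests are proposed in order to assess the overall homogeneity of the prospective and historical cohorts") and gives its purpose: "Results of these investigations can be used to assist in properly weighting the results of the secondary analyses" that use historical data, against the primary analysis in the prospective cohort alone.

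The protocol gives no significance level, number of tests, multiplicity rule or size of relevant difference for these tests. The nearest convention is in section 9.7.1: "All statistical estimates will be reported along with corresponding 95% two-sided CIs".

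On cohort sizes, section 4.8 says "convenience sample sizes between 40 and 70 participants are expected", and the precision figures in section 9.7.9 are "Based on a convenience sample size of 50 participants in the prospective cohort and the inclusion of approximately 400 historical cohort participants". Section 9.5.1 reports 30 enrolled after two years, against 600 originally planned.

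Two other safeguards are planned whatever the tests show: descriptive summaries of the historical cohort in formats similar to those for the prospective cohort (9.7.9), and adjustment for observed characteristics (9.9.2). The adjustment list in section 9.7.6.2 is "alpha-fetoprotein (AFP) level, albumin level, platelet count, MELD score, age in years, gender, diabetes status", alcohol use, HCC treatment modality and study centre.

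**The concern.** Homogeneity is the null hypothesis, so the result that would support leaning on B and C is a failure to reject. Whether a test rejects depends on the prospective sample size as well as on the imbalance. For a fixed imbalance, and so a fixed potential for bias, the cohorts look more alike as recruitment falls. That is also when the pooled analyses become most attractive. At 50 patients and a 35% annual recurrence rate, section 9.5.1 gives the primary analysis an interval of 0.39 to infinity, while section 9.7.9 gives the pooled analysis 0.62 to 1.69.

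Imbalance between the cohorts matters because cohort and exposure are closely aligned. All DAA-exposed time is prospective, and at 50 plus 400 the historical patients, who are never exposed, make up 400/450 = 89% of the pooled sample. The sources also differ by design: Italian centres, diagnosis after 2007 and a last verified update in December 2016, against five countries with data collection from 2018.

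Adjustment handles listed covariates. It does not reach characteristics recorded but not listed, such as the tumour characteristics that section 9.7.9 says the historical database holds.

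**Working it through.** The protocol states no power or error rate for these tests, so there is no figure to reproduce.

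**Inputs.** Historical patients: 400 (9.7.9). Prospective patients: 40 to 70 (4.8), 50 as the central case (9.7.9), with 30 (enrolled so far) and 600 (original plan) from 9.5.1. Assumed: two-sided 5% level, matching the 95% interval convention; imbalance of 0.2 to 0.5 SD; 9 to 14 tests. The 9 are the patient-level covariates in 9.7.6.2, and adding study centre makes 10.

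**Miss rate per test.** For a standardised difference d, SE = sqrt(1/n + 1/400) and miss rate = 1 − Φ(d/SE − 1.96). At n = 50, SE = sqrt(0.0200 + 0.0025) = 0.15.

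| d (n = 50) | d/SE | Miss rate |
|---|---|---|
| 0.2 | 1.33 | 74% |
| 0.3 | 2.00 | 48% |
| 0.4 | 2.67 | 24% |
| 0.5 | 3.33 | 8% |

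The difference detectable with 80% power is (1.96 + 0.84) × 0.15 = 0.42 SD.

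**The same 0.3-SD imbalance at other prospective sizes.**

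| n | SE | Miss rate |
|---|---|---|
| 30 | 0.189 | 65% |
| 40 | 0.166 | 56% |
| 50 | 0.150 | 48% |
| 70 | 0.130 | 36% |
| 600 | 0.065 | 0.4% |

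**Binary factor,** 30% historical against 45% prospective, n = 50: SE = sqrt(0.45 × 0.55/50 + 0.30 × 0.70/400) = 0.074; 0.15/0.074 = 2.03; miss rate 47%.

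**False alarms.** Per test: 5%. At least one among k independent, uncorrected tests: 1 − 0.95^k = 37% (k = 9), 40% (k = 10), 51% (k = 14). If the test statistics are correlated at 0.3, simulation gives about 33%, 35% and 44%. A single global test gives 5%. A Bonferroni correction for 10 tests lowers power at 0.3 SD to Φ(2.00 − 2.81) = 21%, so correcting for multiplicity makes the misses worse.

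**Check on a fixed cut-off as the replacement.** A rule that flags any observed standardised difference above 0.2 would, at n = 50, flag a truly balanced covariate with probability 2 × (1 − Φ(0.2/0.15)) = 18%, and would miss a true 0.3-SD imbalance with probability Φ((0.2 − 0.3)/0.15) = 25%. A bare cut-off is therefore not a clean remedy. An interval is more informative: its half-width is 1.96 × 0.15 = 0.29 SD, which shows directly how little a near-zero estimate rules out.

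**The case against.** The strongest reply is that little hangs on these tests. They may only assist the weighting. No estimate changes with their result, the primary analysis does not use historical data, and adjustment is unconditional. Section 9.9.2 already warns of systematic differences, changes in treatment and imaging, and residual confounding, and section 9.9 states a preference for the internal comparator. Similar-format summaries will let a reader see the size of an imbalance. Both cohorts are BCLC Stage A, and MELD score and albumin are in the model. Section 9.7.6.3 permits exploring additional covariates for the primary analysis, which Secondary B mirrors. The level and list of tests would normally sit in the SAP. All of this stands, and it limits the point. It does not remove it, because the protocol itself selects the tool and states its use.

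Four stronger readings are tempting, and the documents do not support them:

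- **False alarms are as frequent as misses.** This sets a per-test miss rate beside a rate across all tests. Per test it is 5%; about half is reached only with some 14 independent, uncorrected tests, and the protocol does not say how many will be run.
- **The protocol equates non-rejection with comparability, or relies on the tests alone.** Neither is stated.
- **The tests were sized for 600 patients.** No section says so; the 600 row above only illustrates dependence on sample size.
- **A missed imbalance would seriously distort Secondary B.** The documents give no prognostic strengths. If an unadjusted factor had a hazard ratio of 1.65 per SD (an assumption), a 0.3-SD imbalance would shift the log hazard by 0.3 × ln 1.65 = 0.15, about 16%. The stated interval of 0.57 to 1.82 at a 25% recurrence rate implies a standard error of ln(1.82/0.57)/3.92 = 0.30, so this is about half a standard error.

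**Conclusion.** The point holds in a limited form. Tests of a homogeneity null are a poor guide to how far Secondary B and C can be trusted, because at 40 to 70 prospective patients a non-significant result is compatible with imbalances of a size one would want to know about. The miss rate for 0.3 SD is 56% at 40 patients and 36% at 70.

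These figures rest on an assumed two-sided 5% level and on imbalance sizes that the protocol does not give. Readers who regard only 0.5 SD as relevant will find the tests adequate at 50 patients. The practical exposure is confined to characteristics outside the fixed covariate list and to the interpretation of two secondary objectives. A change is worthwhile because a better method needs only data already planned for the descriptive tables.

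**What to change.** In sections 9.7.9 and 9.9.2:

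- Base the comparability assessment on standardised differences with 95% confidence intervals for every baseline characteristic available in both cohorts, and report them beside the B and C results.
- State that p > 0.05 will not be taken as evidence of homogeneity.
- Add one sensitivity version of Secondary B that includes a small number of prognostic characteristics outside the model showing a material imbalance. Judge this on the estimate with its interval and on prognostic relevance, not on a bare 0.2 cut-off. Keep the number small because events will be few.

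Do not ask for balance after adjustment in Secondary B. It is a regression-adjusted Cox model without weights, so that quantity is undefined there, and the weights used for C model the start of DAA therapy and not cohort membership.

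The cost is a wording change, one table and one sensitivity model. Some chance imbalances will be displayed and will need comment.

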9.7.10. Exploratory Objective Analysis Using the Historical Cohort

A non-comparative descriptive summary of the cumulative risk of HCC recurrence over time will be provided for the historical cohort alone. Estimates of cumulative incidence will be provided for 3, 6, 9, 12, 18, and 24 months.

9.8. Quality Control

The DAA-PASS database will be maintained by TPS. Data will be collected as detailed in Section 9.4. The database will be validated in accordance with the procedures of TPS. Data quality will be further ensured through electronic checks, source data verification activities, and clinical monitoring (see Section 10.4). The process will include ongoing assessment of the database to evaluate trends, site performance, and performance of staff (including those abstracting, processing, and monitoring data).

Statistical analyses will be documented in a formal SAP (see Section 9.7). For any data analyses completed, the data used in the analysis will be archived. Analyses will be validated through independent programming.

9.9. Limitations of the Research Methods

Considerations in the choice of study design

A prospective, non-randomized cohort study was chosen and within this cohort the optimal study design to address the research question is being justified hereafter. Considerable effort was given to determining the best methodological approach with which to compare rates of HCC recurrence in the presence and absence of DAA treatment. The conceptual goal of the observational study design is similar to that of a randomized clinical trial: to ensure that patients with DAA exposure are as similar as possible to patients with no DAA exposure with regard to factors related to the outcome (HCC recurrence).

An important challenge of observational studies of drug effects is the identification and mitigation of sources of bias, including confounding (e.g., by indication/channeling bias, etc.), which results from the absence of randomized treatment assignment. Therefore, a major component of developing such a prospective study is careful consideration of potential sources of bias and development of an optimal study design with appropriate inclusion and exclusion criteria and analytical plans using pharmacoepidemiologic methods to address likely bias that may jeopardize the validity of the effect estimate observed.

Two sources of bias were considered in determining the appropriate study design for comparative evaluation: 1) selection bias (bias arising from selection of patients with DAA exposure and patients with no DAA exposure from different source populations) and 2) confounding by indication (i.e., channeling bias or bias arising from differences between patients with DAA exposure and patients with no DAA exposure that impact the underlying risk of recurrence but is not due to DAA treatment).

To minimize selection bias, the use of data from a single prospective cohort of patients is preferable to the use of an externally derived comparator because the former approach increases the comparability of DAA exposure and no DAA exposure, even for factors for which identification or measurement are challenging or infeasible¹⁷. It has been shown that there is substantial heterogeneity in HCC recurrence rates between studies, due to patient level and study level factors. This further supports the use of an internal comparator to reduce selection bias affecting the estimated DAA effect. Additionally, the heterogeneity of recurrence rates and the various identified and potentially unmeasurable predictors of recurrence risk further illustrates

the need to utilize a design with internal comparator in order to estimate the effect of DAA therapy on HCC recurrence risk.

To mitigate confounding by indication to treat HCV with DAAs, several points were considered. The bias to treat HCV with DAAs exists, regardless of whether an internal contemporary or external historical comparator is used (i.e., it is independent from consideration of selection bias). It is, however, easier to control for confounding with an internal comparator as data on patients and confounders will be collected in a similar manner between the 2 groups. Lastly, as sufficient variability exists in clinical practice regarding timing of DAA use, this allows for an internal HCV no DAA exposure comparator.

For the reasons outlined above, the primary analysis in this study is based on the prospectively collected data in DAA-PASS, comparing DAA-exposure vs. contemporary no DAA exposure time and adjusting for baseline covariates. However, although an internal contemporary comparator is preferable, secondary analyses will be conducted to estimate the risk of HCC recurrence associated with DAA therapy relative to no DAA therapy in a pooled dataset that includes data for patients from the prospective study as well as from patients from a historical cohort. This pooled data approach will expand the amount of HCV no DAA exposure person-time, providing a clearer picture of the risk of early HCC recurrence associated with DAA exposure, and also provide an opportunity to characterize the risk of HCC recurrence in HCV-infected patients prior to the introduction of DAAs.

9.9.1. Limitations of Prospective Model and Study Design

The proposed study design was selected based on the expectations of DAA therapy, how HCC recurrence is assessed, and the expected HCC recurrence rate. This study does have limitations because the DAA therapy is not pre-specified and may vary in a manner that affects the precision of estimators. Further, time-dependent covariates may not be completely captured if they are not part of standard of care. Underlying non-ignorable censoring mechanisms, particularly due to potentially high rates of liver transplantation, could potentially bias study results or could reduce precision.

These biases may exist regardless of whether an internal contemporary (i.e., independent from consideration of selection bias) or external historical comparator is used. The use of an internal comparator allows for easier control since data on participants and confounders will be collected in a similar manner between the 2 groups. Factors that differ between patients treated with DAAs and those untreated or not yet treated, may be static (baseline) factors such as demographics and HCC treatment modality or time dependent confounders such as those that occur or change after baseline and which predict DAA treatment and HCC recurrence.

To address the limitations in the study design, especially given that this is a safety study, sensitivity analyses will be used to evaluate the robustness of the primary results to reasonable perturbations of the methods and assumptions used, measures of goodness of fit will be examined, and auxiliary supportive analyses will be used to aid interpretation of the study.

